The initial contact with the potential participant is a call to ask the participant if they would like more information about the study after the study has been introduced by their provider. If they say yes, a brief explanation about the study is provided. They are asked if they have questions and are asked if they would to receive a copy of the consent as an informational packet that they can discuss with family members and their caregiver. They are then asked if we can call them in follow -up after they receive the consent.

The study screening and research procedures will take place at the University of Washington Maternal Infant Care Clinic and other ancillary OB and neighborhood clinic sites of the University of Washington including: Northwest and Montlake Campuses, local Neighborhood clinics, as well remote clinics (Arlington and Yakima OB Clinics). If possible, the visit will be performed in person, but, given the increase in telehealth visits during

the COVID pandemic, if a potential participant is unable to couple the screening visit and/or research visits with standard OB appointments, then televisits for the research visits will be offered.

Population:

We propose to perform an observational prospective study that will involve 100 subjects with confirmed gestational diabetes. There will be 50 participants in the CGM intervention group and 50 in control group. Patients with pre-existing type 1 or type 2 diabetes will be excluded as will overt diabetes (HbA1c >6.5) on initial gestational diabetes screening and/or POC HbA1c. Gestational diabetes screening by oral glucose tolerance test and/ or HbA1c is performed in the OB clinic at initial early prenatal visit or 24-28 weeks based on patient risk. If positive, potential participants will be offered enrollment in the study. Currently the OB department estimates approximately 1400 deliveries annually at Montlake campus and 1100 at our NW campus. This would provide for approximately 2500 pregnancies in one year, with an anticipated 25 pregnancies with gestational diabetes per month. We will have robust population to recruit from. We do not see recruitment as an issue. We will also extend our recruitment to the Arlington and Yakima consult clinics, which see patients from the surrounding areas to increase diversity of our population as for example Seattle's demographics is 11% Hispanic while Yakima is 43%.

E. Statistical Considerations

Sample Size Estimation

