Vital signs will be collected, including height, weight (current and pre-pregnancy), blood pressure, maternal resting heart rate, and estimated gestational age. Maternal ultrasound results will be reviewed if available.

Glucose tolerance test results will be reviewed. Two blood pressure and pulse readings will be taken and HbA1c, both point of care (fingerstick) and HbA1c serum and fructosamine via LabCorp will be obtained. Approximately 1 teaspoon of blood will be drawn. If a patient has an HbA1c documented in the medical record within 2 weeks of the pre-intervention session, then the point of care HbA1c will not be done. The available HbA1c will be used. If they meet all inclusion and exclusion criteria (as outlined above), they will be randomized into either the RT-CGM intervention or control arm at the screening visit.

At the pre-intervention session (week 0) the control GDM group will be asked to wear the CGM blinded for 10 days. They will be asked to continue their usual diet and activity. If, for any reason, the CGM device fails to capture at least 3 days worth of data, the subject may be asked to repeat this measurement at an unscheduled visit. The control group will be given a glucose meter (onetouch) and instructed to follow their obstetric provider's recommendations about checking glucose by meter or if they have not been given instructions or do not remember their instructions they will be asked to check sugars fasting and 1 hour after meals. They will also be given a handout that explains glucose goals and how food and activity effects glucose levels. (Appendix A1,A2). The intervention group will be given RT-CGM and instructed on use with a handout that explains glucose goals and how food and activity effects glucose levels (see handout/Appendix A). The intervention group will also be given a glucose meter (onetouch) and instructed to use for symptoms of low glucose or if they question the accuracy of the CGM. Both groups will be given standard gestational diabetes teaching and nutrition counseling by the RN in clinic and with individual nutrition appointments with the nutritionist, as per current local standard of care.

Participants will be given self-report questionnaires on physical activity, nutrition, sleep history, pregnancy history and overall wellness. Week 0 consenting and baseline data/measurements will take between 1 hour 30 minutes and 2 hours.

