RT-CGM and meter will be downloaded for the intervention group and meter downloaded for the control group. Vital signs, weight and medications and dose will be recorded at each visit and results of maternal ultrasound if available (appendix M).

Between Visits: In the weeks between visits participants will continue their routine OB care with their OB providers. The OB providers may or may not be aware that their patient is participating in the study or have knowledge of their study group allocation. The participants will provide their OB providers the usual blood sugar values that they typically supply to their OB provider. For the control group this will be fingerstick glucose values for fasting and 1-hr post-meals. For the intervention group, this will be a log of the CGM

glucose values at the time of fasting and 1-hr post-meals. The OB providers will not be expected to use the CGM system itself.

Delivery: EMR will be reviewed for maternal and fetal outcomes.

I. Randomization/allotment: Randomization/allotment: Once they have signed the consent form, study participants will be randomized to treatment group. The project will use random, permuted blocks within strata to do this. Two participant factors will be considered in creating the strata: 1) weeks pregnant (14-24 weeks or 28 weeks); and 2) pre-pregnancy BMI (≤ 35 and >35). Thus, the strata will be:

Pregnant 14-24 weeks and BMI ≤ 35

Pregnant >24 weeks and BMI ≤ 35

Pregnant 14-24 weeks and BMI >35

Pregnant >24 weeks and BMI >35 .

Separate randomization lists will then be prepared for each of the above strata, using random permuted blocks generated in SAS 9.4. The lists will be transferred (by the statistician) to a sequence of sealed envelopes with the treatment group noted on a card within.

Since this is a small clinical trial, there is the potential problem of uneven distribution of study participants across the strata. However, we believe we have mitigated this potential by having only 4 strata. Also, this approach works better for this project than other approaches (such as the minimization method) due to the relatively greater level of staffing effort required for those approaches to work.

Source: Pocock SJ. 1983. Clinical Trials. A Practical Approach. Chichester, New York: John Wiley & Sons

J. Study Procedures, Materials and Devices :

Televisits:

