inspect and copy the participant information include the IRB of the University of Washington. A master code linking the unique study numbers with subjects' identifying information will be kept by the Principal Investigator or by the Project Officer in a locked file cabinet. Additionally, all data collected by coordinators will be entered and managed through the encrypted Research Electronic Data Capture (REDCap) system maintained at University of Washington. All data is de-identified with no personal health information entered (PHI). REDCap was developed specifically around HIPAA security guidelines. REDCap has been disseminated for local use at more than 940 other academic/non-profit consortium partners in 75 countries. REDCap servers are housed in a local data center at CNMC, and all web-based information transmission is encrypted. This system is accessed through a secure login and password. Only the RedCap database coordinators and study staff will have access privileges to the University of Washington data set and will be strictly prohibited from sharing passwords. All will undergo the standardized authorized training provided by the REDCap team. Staff will maintain files in password-protected documents on HIPAA-compliant servers. REDCap programmers build in quality controls for the data that will be collected according to their stringent protocols. Data will be stored for 3 years after study completion for possible re-analysis and sub-group analysis that the clinical team may determine to be useful. More information about the consortium and system security can be found at <http://www.projectredcap.org>. [name] and her research team will destroy the informed consent, research source documents, data files, and master code 3 years after the completion of the study. This will allow time for the PI and collaborators to reexamine the data as needed in the revision process for manuscripts submitted to peer-reviewed journals.

All information that the study subjects provide study personnel is for research purposes only and, as such, names and any other identifying information will not be reported or published in papers, presentations, or proposals that result from this research.

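### Section I leaves enrolling staff able to predict, or gain early access to, the next assignment: pre-filled envelopes, no rule on custody or block size, and past assignments open to staff

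*Combined protocol and SAP*

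**What the plan says.** Section I (Randomization/allotment) forms four strata from weeks pregnant and pre-pregnancy BMI. "Separate randomization lists will then be prepared for each of the above strata, using random permuted blocks generated in SAS 9.4". It continues: "The lists will be transferred (by the statistician) to a sequence of sealed envelopes with the treatment group noted on a card within". The supplied text gives no other concealment measure. It does not give the block size, whether the size varies or is withheld from staff, whether the envelopes are opaque or numbered, who holds and opens them, where they are kept, or whether openings are logged.

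Other sections bear on this:

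- **Timing.** Section I places randomisation after signed consent. Section H (Screening/Pre-Intervention Visit) makes it conditional on meeting all criteria: "they will be randomized into either the RT-CGM intervention or control arm at the screening visit".
- **Past assignments are known.** Under Section J (Medical Devices), study staff fit the first sensor in both groups and train the intervention group, and the coordinator fits the control group's sensors. Under Section S, the study number carries the arm and a running count within it (DMC-001, DMCGM-001).
- **The same team controls entry.** The coordinator pre-screens clinics and contacts candidates (Section D), and study staff arrange the screening appointment (Section H).
- **Several places, four lists.** Section D names several campuses, neighbourhood clinics, Arlington, Yakima and televisits. Site is not a stratum, and the plan does not describe how one sequence per stratum serves all of them.

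**The concern.** Concealment protects the comparison only while the person enrolling cannot know the next arm. Here that person knows the earlier arms, the strata are written in the protocol, and the full future sequence exists on cards. Two routes are left open. The first is prediction: in a permuted block, earlier assignments carry information about later ones. The second is access: the plan names no custodian, storage place or opening log, so nothing in it rules out a card being read early or used out of turn.

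Staff who foresaw the arm could bring forward or delay women they thought suited to RT-CGM. Scheduling gives them room to do so, as does one eligibility criterion that needs judgement (possible preterm delivery, Section F). The arms would then differ in prognosis before treatment starts. Every between-arm aim would share that bias: HbA1c, CGM metrics, medication and delivery outcomes. Baseline adjustment could not fully remove it, because the choice may rest on unrecorded factors such as motivation.

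**Working it through.** The plan states no figure for predictability, so there is nothing to reproduce.

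**Inputs from the documents:** 1:1 allocation, 50 per arm, four strata, permuted blocks.

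**Assumed:** block size (2, 4, 6, or a 4/6/8 mix); strata of 40/30/20/10; a prognosis shift d of 0.2, 0.3 or 0.5 SD in the direction of the foreseen arm; and, unless stated, staff who see the whole history of the stratum.

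**Step 1: certain assignments, known fixed block of 4.** The fourth place is always certain. The third is certain when the first two match (probability 1/3). That is 1 + 1/3 = 4/3 per complete block, or 33.3%. The assumed strata hold 10 + 7 + 5 + 2 = 24 complete blocks plus two half-blocks with no certain place, so 24 × 4/3 = 32 of 100 women (32%). In simulation, blocks of 2 and 6 give 50% and 23%. An undisclosed 4/6/8 mix gives about 0.2%.

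**Step 2: guessing the arm with more places left, block of 4.** The chances of a correct guess by place are 1/2, 2/3, 2/3 and 1, which sum to 2.833 (70.8% of a complete block). With the half-blocks: 24 × 2.833 + 2 × (1/2 + 2/3) = 70.3, or about 70%. Simulation gives 75% for blocks of 2, 67% for 6, and 67% for the 4/6/8 mix.

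**Step 3: false difference if staff act only on certain assignments (block of 4).** On average 16 women of 50 in each arm are shifted, upwards in one arm and downwards in the other. The difference is 2 × (16/50) × d = 0.64d, which is 0.128, 0.192 and 0.320 SD.

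**Step 4: error rate.** The standard error of the difference is √(1/50 + 1/50) = 0.2 SD, so z = 0.64, 0.96 and 1.60. The two-sided error is Φ(z − 1.96) + Φ(−z − 1.96), which is 9.8%, 16.0% and 36.0%. A simulated two-sample t-test gives 9%, 16% and 34%. It is slightly lower at the largest shift because the shifts also widen the spread within arms.

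**Step 5: the same with guesses, undisclosed 4/6/8 mix.** If a share p of guesses is right (ties counted as half), the difference is 2(2p − 1)d. With p = 0.67 this is 0.68d, which is 0.136, 0.204 and 0.340 SD. The Step 4 formula gives 10.4%, 17.5% and 39.8%. Simulation gives about 11%, 17% and 37%.

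**Simulated two-sided error, nominal 5%**

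| Scenario | d = 0.2 | d = 0.3 | d = 0.5 |
|---|---|---|---|
| Fixed 4, act on certain assignments | 9% | 16% | 34% |
| Fixed 4, act on guesses | 12% | 20% | 49% |
| Mix 4/6/8, act on certain assignments | 5% | 5% | 5% to 6% |
| Mix 4/6/8, act on guesses | 11% | 17% | 37% |

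With three assumed sites, each seeing only its own history and acting on guesses, the error is about 5% to 7% for fixed or mixed blocks. No row covers early access to the cards. If the cards could be read, every assignment would be knowable whatever the block size.

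**The case against.** The strongest reply is that the concern rests on silence. The envelopes are sealed and form a sequence. The statistician, not the enrolling staff, prepares them. Study numbers run in order of enrolment, which gives a partial check on order. Randomisation follows consent and, in Section H, a check of all criteria, most of which are objective. Leaving the block size out of a protocol that staff can read is also what withholding it would look like. The listed appendices, including the Data and Safety Monitoring Plan, were not available for this review and may describe handling.

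Much of this stands. A reader might infer that envelopes sit at the clinics, or that staff can see the next card. The documents support neither: storage is not stated, and unstated opacity is not transparency. Nor do they show that staff can work out the next arm with certainty, which needs a fixed block size that they know. The error rates are also conditional. The shifts have no source in the documents, and recruitment at several sites works against any one person seeing a stratum's full history.

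Section I also prefers its method to others, such as minimisation, because of staffing effort. That argument does not reach central release, which keeps the same kind of lists and changes only who holds them. Section S does describe REDCap for data entry only, so its use for randomisation is an assumption. Release by the statistician is the alternative.

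What remains is that the plan gives no rule closing either route, although staff know past assignments and control who is booked and when.

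**Conclusion.** The concern holds as a weakness in what the plan prevents, not as evidence that allocation is or will be subverted. Under the full-history assumption, a known fixed block of 4 makes about 32% of assignments certain, and acting on them gives an error of about 9% to 34% for shifts of 0.2 to 0.5 SD. If sites see only their own history, the error stays at about 5% to 7%.

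A reader might also infer that mixed block sizes restore the 5% level. They do so only if staff act solely on certain assignments. If staff act on guesses, correct about 67% of the time against 70% for fixed blocks of 4, the error is still about 11% to 37%. Varied blocks are therefore a modest gain. The main gain comes from making the next assignment impossible to reach or reorder. This is a cheap improvement that the sponsor should make.

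**What to change.** In Section I, replace the envelope sentence with text to this effect:

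> Lists use randomly varying block sizes known only to the statistician. Assignments are held centrally, in REDCap or by the statistician, and are released one at a time, with date and time recorded, after consent, confirmed eligibility and stratum have been entered.

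Also align Section I, which ties randomisation to signed consent, with Section H, which requires all criteria to be met first. Women already randomised keep their assignment, and the new lists apply to those not yet randomised.

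REDCap is a natural place for the release step, since "all data collected by coordinators will be entered and managed through the encrypted Research Electronic Data Capture (REDCap) system maintained at University of Washington".

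The cost is a few lines of SAS code, a wording change, and an access or message step at the week 0 visit. Larger varied blocks may leave slightly more imbalance between arms in a small stratum. No patients, visits or procedures are added. If the sponsor already works this way, a few sentences in Section I are enough.

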The HbA1C outcome was used for the sample size calculation. Since we are collecting HbA1C every 8 weeks, we are able to leverage the repeated measures design in the estimation of the sample size needed for this study. This allows us to gain efficiency and reduce the number of subjects needed. Thus, for an effect size 'f' of 0.14, which is between small (0.10) and medium (0.25), an alpha of 0.05 and power of 0.80, we need a total of 92 study subjects. Allowing for some attrition in study subjects, we are planning to enroll 100 patients.

Note that this type of sample estimation requires that we specify the variance across observations (sphericity) and the correlation across observations. We specified both at 0.60. We calculated sample size using G*Power.

Data Analysis Plan

The data analysis will start with completion of the **CONSORT** diagram, with an analysis of differences between those who completed the study and those who did not (t-tests and chi-square tests, as needed, comparing basic demographics and baseline health characteristics), so that the researchers in this area can understand the extent to which our study contains bias.

Next, we will calculate summary statistics (means, medians, proportions, etc.) of all baseline measurements, overall and by study arm, so that we can fully characterize the study cohort.

Using the CGM data, we will graph each participant's trajectories over time and review each, examining for major patterns in the trajectories. Note that typically statistical analyses emphasize homogeneity in the data; however, this approach will allow for understanding of heterogeneity. As part of this examination of the CGM data, the analysis will calculate each participant's measures of glycemic variability (such as mean amplitude of glycemic excursions, coefficient of variation, etc.), HbA1C values, and fructosamine values and overlay them on each graph. This part of the analysis is predominantly exploratory.

For the statistical, hypothesis-testing examinations of HbA1C, fructosamine, CGM readings, and glycemic variability across key time points, we will conduct mixed models (i.e., multilevel model) analyses, which will allow us to quantify within-between interactions, or changes within subjects over time and differences across groups. These models can also include multiple independent variables/covariates.

F. Inclusion/Exclusion Criteria

Inclusion criteria:

1. Pregnancy and Gestation \leq 30 weeks
2. Singleton pregnancy

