- Participants with applicable smart phones may have CLARITY® push notifications on the CLARITY® mobile app about weekly time in range comparison enabled during the study.

- For app users, the “Share and Follow” functionality will be discussed and encouraged (i.e. the study participants are able to invite followers to review their glucose levels).

- For participants using the receiver only, the receiver will be downloaded into the CLARITY® clinic account at each visit. CGM data and reports. RT CGM-Participants will also keep a logbook of their blood sugars for their provider to review.

Control Group

The participants of the control group will perform self-monitored blood glucose testing with a study-provided blood glucose meter, including testing supplies. They will perform capillary blood glucose monitoring as routinely used for patients with GDM, i.e., at least four capillary blood glucose values daily including measurements in a fasting state as well as 1h after starting each meal. The study participants will keep a logbook of their glucose values

Each participant of the control group will be assigned a study blood glucose meter to measure and store their blood glucose values during the study.. A commercially available desktop software used in conjunction with the glucose meter for blood glucose monitoring will be utilized for downloading the meter data at each visit ensuring that dates and times are correct. Blood glucose meters used by the control group will be assessed to establish frequency of testing (overall and per week) as well as percentage of days with less than four measurements per day.

Subjects who got randomized to the control group then decided to withdraw from the study and discontinue their participating in the study will receive an email asking them to fill out a survey questionnaire to explain the main reason and any other reasons for withdrawal from the study. The survey will be sent to subjects’ email through a link from Redcap and it won’t take more than 10 minutes to complete.

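### Reasons for withdrawal are surveyed in the control arm only, and the completer versus non-completer comparison is not specified by arm

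*Combined protocol and SAP*

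**What the plan says.** Section J (Study Procedures), under Control Group, describes an emailed REDCap survey for "Subjects who got randomized to the control group then decided to withdraw from the study". They are asked to "fill out a survey questionnaire to explain the main reason and any other reasons for withdrawal from the study". The Intervention Group list in the same section has no such item.

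Section E (Data Analysis Plan) opens: "The data analysis will start with completion of the CONSORT diagram". It adds "an analysis of differences between those who completed the study and those who did not", using "t-tests and chi-square tests, as needed, comparing basic demographics and baseline health characteristics". The stated purpose is that researchers in the field "can understand the extent to which our study contains bias". Arm is not mentioned in that sentence. The next paragraph does mention it, for summary statistics "of all baseline measurements, overall and by study arm".

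The hypothesis tests in section E are mixed models. No missing-data assumption or sensitivity analysis is named. Section D allows dropouts to be replaced until 95 participants are evaluable, with at most 130 recruited.

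**The concern.** Attrition biases a comparison of arms when those who leave one arm differ from those who leave the other. Two things are needed to see this: why women left each arm, and how leavers differ from stayers within each arm. The plan collects the first in a dedicated form for controls only. For the second it leaves open whether arm enters the comparison at all.

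The RT-CGM arm has its own plausible reasons for leaving. It wears a sensor continuously through pregnancy (section J), and section P lists skin reactions and dislike of wearing a device. The questionnaire on CGM experience is given at 34–36 weeks (section K), so a woman who stops earlier would not reach it. The gap therefore also touches Aim 3, on how participants perceive RT-CGM.

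At stake is how well readers can judge attrition, a task the plan sets itself. Replacing dropouts restores the numbers but does not make the arms comparable again.

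**Working it through.** **Inputs from the documents.** 92 participants needed and 100 enrolled (section E); 50 per arm (section D); 95 evaluable and at most 130 recruited (section D). No dropout rate is given, overall or by arm.

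**Attrition implied.** 100 − 92 = 8 non-completers, or 8%. At the limit, 130 − 95 = 35, or 35/130 = 26.9%. The second figure assumes that all 130 are randomized.

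**What the baseline t-test can detect.** With two-sided alpha 0.05 and 80% power, the detectable difference in SD units is (1.96 + 0.842) × √(1/n₁ + 1/n₂).

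| Non-completers | Completers | Detectable difference |
|---|---|---|
| 8 | 92 | 2.802 × √(1/8 + 1/92) = 1.03 SD |
| 14 | 86 | 2.802 × √(1/14 + 1/86) = 0.81 SD |
| 35 | 95 | 2.802 × √(1/35 + 1/95) = 0.55 SD |

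The middle row is an intermediate illustration. This normal approximation is slightly optimistic when one group has only 8 members.

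**What is lost if arm is ignored.** These scenarios are assumed, with 3,000 simulated trials each. Selection is a shift of 0.8 SD in the baseline mean of non-completers. The table gives the proportion of trials in which each test rejects at 5%.

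| Scenario | Arms combined | Arm-by-completion test |
|---|---|---|
| Opposite directions, 65 per arm, 18 and 17 dropouts | 3.7% | 97.9% |
| Opposite directions, 50 per arm, 4 and 4 dropouts | 4.3% | 57.5% |
| Controls only, 65 per arm, 25 and 10 dropouts | 81% | 47% |
| No selection, 65 per arm, 18 and 17 dropouts | 5.2% | 5.2% |

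The first row can be checked by hand. Combined, the non-completer mean is shifted by only (18 × 0.8 − 17 × 0.8)/35 = 0.02 SD, so there is almost nothing to find. The interaction is 1.6 SD with standard error √(1/18 + 1/47 + 1/17 + 1/48) = 0.40, a ratio of about 4.0.

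The third row shows the limit of the argument: when only one arm is selected, the combined test does better than the interaction test.

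**Cost in precision of going by arm.** Within one arm, 4 non-completers against 46 completers give 2.802 × √(1/4 + 1/46) = 1.46 SD. A by-arm comparison at the planned attrition is therefore descriptive and should not be read through its p-values.

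**Reasons for leaving.** No arithmetic applies. Followed as written, the plan yields survey reasons for control withdrawals and none for RT-CGM withdrawals.

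**The case against.** A reader might infer that the plan cannot detect differential dropout at all. The documents do not support that. A CONSORT diagram shows participant flow by arm, and section S puts the arm in every study number, so unequal counts would be visible. A combined baseline comparison can also flag selection confined to one arm, as the third simulated scenario shows.

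A reader might also take it as stated that the comparison combines the arms. Section E says neither that nor the contrary. The contrast with the by-arm baseline summaries makes it a fair guess, but the text only leaves it unspecified.

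A third temptation is to put a bias on the treatment contrast: the difference in dropout rates times the difference between dropouts and completers, for example 0.12 × 0.5 = 0.06 SD. Both factors are assumed. The product describes a completers-only contrast, whereas the plan uses mixed models that can draw on partial follow-up. It also assumes equal selection in both arms, and in that case the CONSORT counts and a combined comparison would supply both factors.

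Finally, the survey is not presented as part of the section E bias check, and the appendix list names an adverse events log and a data and safety monitoring plan that are not supplied. The log may record skin reactions in the RT-CGM arm, but it would not stand in for a survey of reasons. Nor can any table or survey verify that data are missing at random; it can only inform the judgement.

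These points narrow the concern. They leave standing the one-arm survey, the unspecified role of arm, and the weak test.

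**Conclusion.** The point holds in a limited form and is minor. The plan can show how many women left each arm. It cannot compare their reasons between arms, and it could miss opposite selection in the two arms unless the completer comparison takes arm into account. A non-significant baseline test would be weak reassurance: the detectable difference is about 1.0 SD at the implied 8% attrition and about 0.55 SD at the recruitment limit.

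The detectable differences follow from the plan's own totals, with the limit case resting on all 130 being randomized. The simulated rejection rates rest on assumed dropout numbers and an assumed 0.8 SD shift, and they illustrate the mechanism only. No size of bias in the planned mixed-model result can be derived from the documents.

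**What to change.** 1. In section J, send the existing REDCap withdrawal survey to women who withdraw from either arm.
2. In section E, state that dropout counts, timing, reasons and baseline characteristics will be tabulated by arm.
3. Make the completer comparison within arm or with an arm-by-completion term, and report differences with confidence intervals. A comparison with arms combined can stay alongside, since it is the stronger of the two when only one arm is selected.
4. Add one sensitivity analysis of the mixed model that shifts missing outcomes in each arm. Shifting them in controls only would repeat the asymmetry.

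The cost is one more survey link, at most 10 minutes for a few more women, and a short extra analysis. The survey should change first, because reasons not collected at the time of leaving are hard to recover later.
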